1. Subject has an acute illness with or without elevated body temperature (≥ 100.4 °F [38.0 °C]) within 3 days prior to the scheduled vaccination. Subjects may be rescheduled for vaccination at a later date provided that the illness has resolved (body temperature < 100.4 °F [38.0 °C]);
2. Subject has received antipyretics within 4 hours prior to the scheduled time of vaccination. In this case the vaccination should be performed at a later date.

In addition, the following criteria must be met:

1. For a rescheduled **first** vaccination:
 - a. All inclusion and none of the exclusion criteria are met; In case not all of these criteria are met, the subject will be excluded from the study.
 - b. The rescheduled visit should be within the specified time window (i.e. within 21 days after the screening visit). In case a first vaccination cannot be rescheduled

within the specified time window (i.e. within 21 days after the screening visit), the subject might be invited for a rescreening.

2. For a rescheduled **second or third** vaccination:

The rescheduled visit should be within the specified time window.

Booster Phase

Inclusion criteria:

Subjects must meet **ALL** of the following criteria to be eligible for the Booster Phase:

1. Randomization into 180 µg group in the Main Study Phase
2. No relevant protocol deviation* in the Main Study Phase, i.e., included in the PP population for the Day 208 interim analysis of the Main Study;
3. Subject is of good general health, including subjects with pharmacologically controlled chronic conditions;
4. Subject has an understanding of the study and its procedures, agrees to its provisions, and gives written informed consent prior to any study-related procedures;
5. If subject is of childbearing potential:
 - a. Subject has a negative Urine pregnancy test before booster vaccination (Visit 9);
 - b. Subject agrees to employ adequate birth control measures for the duration of the study (please refer to section 6.4).

Exclusion criteria:

Subjects who meet **ANY** of the following criteria are **NOT** eligible for the Booster Phase:

1. Subject met an individual stopping criterion during the Main Study Phase
2. Subject has developed a chronic illness related to Lyme borreliosis (LB), an active symptomatic LB as suspected or diagnosed by a physician, or received treatment for LB within the last 3 months prior to Visit 9;

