- (9) If applicable, HIV test, Lyme borreliosis screening test, serum pregnancy test, clinical chemistry tests, hematology tests, and coagulation tests performed at the study site within the study VLA15-201 is acceptable for study VLA15-202 if within the specified visit window. As such, if test results are available, respective blood samples do not need to be collected again for the present study. Similar, if applicable, a baseline serology sample collected at the study site within the study VLA15-201 is acceptable for study VLA15-202 if within the specified visit window.
- (10) A commercially available Lyme borreliosis screening test will be performed (blood: 4 mL). Serum samples that are tested positive have to be verified by a confirmatory immunoblot. LB test results need to be available before randomization and remain valid for 4 weeks.
- (11) For in-person study visits only.
- (12) A baseline serology sample is taken at the screening visit and might be used for retrospective work-up of suspected AESIs (e.g. analysis of Rheumatoid factor (RF), anti citrullinated protein antibodies (ACPA) etc., as appropriate). (blood: 5.0 mL). If applicable, a baseline serology sample collected at the study site within the study VLA15-201 is acceptable for study VLA15-202 if within the specified visit window.
- (13) In women of childbearing potential. A woman is considered of childbearing potential if fertile, following menarche and until becoming post-menopausal unless permanently sterile. A woman who is considered of non-childbearing potential must be e.g. surgically sterilized for at least 3 months prior to Visit 1 (e.g. by hysterectomy, bilateral

salpingectomy, bilateral oophorectomy, trans cervical sterilization), or postmenopausal for at least one year prior to Visit 1. For serum pregnancy test: tests that were performed in study laboratory within visit window and where results are available at study visit are acceptable.

(14) At vaccination visits, all samples have to be obtained before vaccination. Pregnancy results and urinalysis must be available before vaccination.

(15) Creatinine, sodium, potassium, calcium, aspartate aminotransferase (AST), alanine aminotransferase (ALT), alkaline phosphatase, bilirubin, CRP (blood: 8.5 mL). Test results from this study visit do not need to be available before vaccination. Tests that were performed in study laboratory within visit window and where results are available at study visit are acceptable.

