- Instruct subject to immediately inform the site in case subject experiences one of the following:
 - any severe adverse event
 - any symptoms suspicion or diagnosis of Lyme borreliosis, e.g. red or bluish-red patch (≥ 5 cm, indicate location), or joint swelling (indicate which joint).
- Perform scripted safety assessment. Record any unsolicited AEs since the last study visit.

In case the subject visit is performed remotely and the COVID-19 situation allows coming to the site at a later time point, the immunogenicity sample should be taken during an unscheduled visit as early as possible within a maximum time window of 2 months after the V7 remote study visit.

Visit 8, Day 545/ Month 18 (+/- 28 days):

This visit should preferably be conducted as an in-person visit. If an in-person is not feasible due to COVID-19, e.g. travel restrictions, local recommendations, circumstances at the study site's location that prohibit an in-person visit, or if the PI believes that the subject's safety and well-being might be jeopardized with an in-person visit at the study site due to COVID-19, the visit should be conducted remotely (e.g., phone/ video call).

For in-person visits:

- Document any changes to concomitant medication/treatments including vaccination(s) since the previous study visit.
- Perform symptom-driven physical examination.
- Review and collect Memory Aid, including verification of entries with the subject.
- Record any unsolicited AEs since the last study visit.
- Laboratory tests:
 - Lyme borreliosis screening test: For serological screening on infection with Lyme borreliosis, a commercially available Lyme borreliosis screening test will be performed. Serum samples that are tested positive will be verified by a confirmatory immunoblot.
 - Urine pregnancy test: In women of childbearing potential.
 - Clinical Chemistry: Creatinine, sodium, potassium, calcium, aspartate aminotransferase (AST), alanine aminotransferase (ALT), alkaline phosphatase, bilirubin, CRP.
 - Hematology: Hemoglobin, hematocrit, erythrocyte count, white blood count, platelets.
 - Urinalysis (standard urine dipstick): pH, specific gravity, leucocytes, nitrite, protein, glucose, ketones, urobilinogen, bilirubin, erythrocytes.
- Collect immunogenicity blood sample.

For remote visits

- Document any changes to concomitant medication/treatments including vaccination(s) since the previous study visit.

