- Review of Memory Aid: Ask subject to read through memory aid/ AE sections of subject diary if previous visits were conducted as remote study visits, or to mail or email pictures of the memory/diary entries upfront to aid the discussion.
- Perform scripted safety assessment. Record any unsolicited AEs since the last study visit.
- Inform subjects of the possibility of an unscheduled visit within 1 month after the remote visit for immunogenicity sample collection, if the COVID19 situation allows.
- If the COVID-19 situation allows coming to the site for an unscheduled visit within 1 month after the remote visit: take immunogenicity sample.

The following procedures are performed for subjects enrolled in the Booster Phase:

Visit 9, Month 18 (Date of Visit 8 (+ 2 max. months)):

Visit 8 and Visit 9 should be combined in one visit if possible; otherwise the time between Visit 8 and Visit 9 should be kept as short as possible (preferably maximum of one month apart). If the COVID19 pandemic mandates, the subject has the possibility to perform the study visit within 2 months after Visit 8. If both visits are scheduled on the same day, all procedures from Visit 8 have to be performed prior to performing procedures from Visit 9.

Signed and dated informed consent for the Booster Phase must be obtained before any study specific procedures are undertaken.

- Check of inclusion and exclusion criteria.
- Check vaccination delay criteria.
- Document any changes to concomitant medication/treatments including vaccination(s) since the Visit 8.
- Perform symptom-driven physical examination, measure vital signs (systolic and diastolic blood pressure, pulse rate) in seated position and at rest, measure oral body temperature (vaccination should be postponed in case of an acute febrile illness).
- Laboratory tests (samples to be taken prior to vaccination):
 - Lyme borreliosis screening test (only to be performed if Visit 9 is later than 1 month after Visit 8): For serological screening on previous infection with Lyme borreliosis, a commercially available Lyme borreliosis screening test will be performed. Serum samples that are tested positive will be verified by a confirmatory immunoblot.
 - Urine pregnancy test: In women of childbearing potential.
 - Urinalysis (standard urine dipstick): pH, specific gravity, leucocytes, nitrite, protein, glucose, ketones, urobilinogen, bilirubin, erythrocytes.

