For Visit 6-8, Visit 10-12, in case visit is performed remotely, subject should be asked to read through the diary/memory aid, or to mail or email pictures of the diary/memory aid entries to aid the discussion. Subject should be instructed to continue using the diary/memory aid for documenting AEs and to bring the diary/memory aid along for the next study visit, if applicable.

After Subject Diary verification, the clinician performs a severity assessment on the basis of the information provided by the subject in the Subject Diary. The severity assessment is based on the grading scale in Table 10 below. Severity categories in this table are NOT identical to the categories provided in the Subject Diary. The investigator or authorized delegate enters diary data and his severity assessment into the eCRF.

For solicited AEs which are serious and/ or medically attended, the investigator carries out more detailed assessments as performed for unsolicited AEs (causality, outcome, action taken) and documents them in the eCRF.

For solicited local and systemic AEs persisting beyond Day 6 after vaccination, stop date is also documented in the eCRF.

Any unsolicited AE documented on the Subject Diary should be documented and assessed as outlined in section 8.4.

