9.4 Safety Analysis

Main Study Phase:

All subjects entered into the study who received at least one vaccination (safety population) will be included in the safety analysis. Safety tabulations will generally be provided separately for solicited AEs and unsolicited AEs, and for both types of AEs combined. 95% confidence intervals according to Altman will generally be provided for all AE rates. Further details in addition to the outline below will be provided in the SAP.

The number and percentage of subjects with any AE, any unsolicited AE, any related unsolicited AE, any SAEs, any AESI, any related SAEs, any medically attended AE and any AE leading to withdrawal from further treatment, up to Day 208 and up to Day 545, will be presented for each treatment group, overall and by system organ class/preferred term. Differences between both dose (VLA15 135 µg w/ alum and VLA15 180 w/ alum) groups and the placebo group will be assessed for significance using Fisher's exact (Fisher-Freeman-Halton) test, whereby a significant overall test will be amended by pair-wise tests. In addition, the number and percentage of subjects with any AE, any unsolicited AE, any related unsolicited AE, any SAEs, any related SAEs, any AESI, any medically attended AE and any AE leading to withdrawal from further treatment will be presented grouped by onset within 28 days after the first, the second or the third vaccination.

The number and percentage of subjects with solicited local and systemic AEs within 7 days after each vaccination and within 7 days after any vaccination will be tabulated. Differences between treatment groups will be assessed for significance using Fisher's exact test, a significant overall test will be amended by pair-wise tests. The occurrence of solicited local and systemic AEs will also be tabulated by Subject Diary day.

Changes in laboratory values from study entry to end of treatment/follow-up will be analyzed descriptively and will be part of the unsolicited AE evaluation only in case of clinically relevant deviations. The frequencies of subjects with laboratory assessments outside the normal range, and with abnormal laboratory parameters falling into the grade 0 vs. 1 through 4 will be calculated. The frequency of subjects with urinalysis results according to the test manufacturer's results categories will be calculated.

It will be defined in the SAP which safety analyses will also be repeated stratified by baseline *B.b. s.l.* serostatus and by age.

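### Visit 8 laboratory findings may be ascertained more fully in the 180 µg arm, because only that arm has an in-person booster visit to combine with it; the planned Day 545 comparison takes no account of this

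*Protocol*

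**What the plan says.** **Visit 8 mode.** For every arm, section 4.2.3 states "This visit should preferably be conducted as an in-person visit". Remote conduct is allowed only for COVID-19 reasons, one of which is the investigator's view of the subject's safety.

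**What a remote Visit 8 loses.** In Table 3, footnote 11 ("For in-person study visits only") is attached at Visit 8 to chemistry, hematology, urinalysis, the Lyme screening test, the urine pregnancy test and the symptom-driven examination. The only catch-up is for immunogenicity: "Inform subjects of the possibility of an unscheduled visit within 1 month after the remote visit for immunogenicity sample collection". Memory Aid review, the scripted safety assessment and recording of unsolicited AEs continue by phone or video.

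**Who has a Visit 9.** The first booster inclusion criterion is "Randomization into 180 µg group in the Main Study Phase", and membership of the Day 208 per-protocol population is also required. Table 4 lists Visit 9 as in-person. Section 8.3.1, on remote conduct, names the other late visits and not this one: "For Visit 6-8, Visit 10-12, in case visit is performed remotely". On the link between the two visits, section 4.2.3 says "Visit 8 and Visit 9 should be combined in one visit if possible". They may be up to two months apart if the pandemic requires it.

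**Who knows.** Under section 4.2.10, sites receive the list of subjects to invite, all from the 180 µg arm, shortly before Visit 8.

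**The comparison.** Section 9.4 says that subject counts for AE categories "up to Day 208 and up to Day 545, will be presented for each treatment group". Arms are compared by Fisher-type tests, with pair-wise tests after a significant overall result. Sections 4.1 and 8.4 count clinically relevant laboratory abnormalities as unsolicited AEs.

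**The concern.** A between-arm comparison of AE frequencies assumes that each arm was searched with the same intensity. At Visit 8 this may fail. An eligible 180 µg subject has a reason to come to the site that no 135 µg or placebo subject has. Table 4 footnote 9 strengthens it: if Visit 9 falls within one month of Visit 8, the Visit 8 sample serves as the pre-booster sample. The site also knows which subjects these are when the visit mode is settled.

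If some Visit 8s are remote, silent laboratory abnormalities would be found more often in the 180 µg arm at equal true risk. That is the dose taken forward, so what is at stake is the accuracy of its safety profile to Month 18. For a remote Visit 10, section 4.2.3 provides a mobile nurse or a make-up visit for safety laboratories. Visit 8, which closes the comparison of the three randomised arms, has no such provision.

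**Working it through.** The protocol gives no figure on this point. Its one formal calculation (80% power for Day 208 titers) does not enter.

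**Inputs from the protocol**
- Arm sizes: 97 (135 µg), 98 (180 µg), 51 (placebo); section 1.4.3.2.
- Booster participants: at most 81; section 9.6. 81/98 = 0.827.

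**Assumed, because the protocol does not give them**
- r, the share of Visit 8s that would be remote without a booster visit: 0, 10, 30, 50%.
- q, the probability that a tested subject has a reportable finding detectable only in person at Visit 8: 2, 5, 10%.
- a, the share of otherwise-remote booster subjects who attend Visit 8 in person because of Visit 9. Setting a = 1 gives the upper bound.

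**Step 1: coverage of in-person Visit 8 procedures**

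135 µg and placebo: 1 − r.
180 µg: (17/98)(1 − r) + (81/98)(1 − r(1 − a)) = 1 − r + a·r·(81/98).
Gap = a·r·(81/98).

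With a = 1:

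| r | 180 µg | 135 µg and placebo | Gap (points) |
|---|---|---|---|
| 0 | 100% | 100% | 0 |
| 10% | (81 + 15.3)/98 = 98.3% | 90% | 8.3 |
| 30% | (81 + 11.9)/98 = 94.8% | 70% | 24.8 |
| 50% | (81 + 8.5)/98 = 91.3% | 50% | 41.3 |

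With a = 0.5 every gap halves; at r = 30% it is 12.4 points.

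**Step 2: excess in the share of subjects with a Visit 8-only finding**

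Excess = q × gap, with equal true risk and a = 1:

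| r | q = 2% | q = 5% | q = 10% |
|---|---|---|---|
| 10% | 0.17 | 0.41 | 0.83 |
| 30% | 0.50 | 1.24 | 2.48 |
| 50% | 0.83 | 2.07 | 4.13 |

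These are percentage points. They are ceilings for AE rates, because section 9.4 counts subjects: someone already counted in a category adds nothing.

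**Step 3: effect on the test**

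The rejection rate of a two-sided 5% Fisher's exact test was enumerated for 98 against 97 subjects, on Visit 8-only findings and with a = 1. It stays below 5% in every combination except q = 10% with r = 30% (6.3%) and q = 10% with r = 50% (13.8%). For reference, it is 3.7% at q = 10% with r = 0.

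**Step 4: what the route does not reach**

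The primary endpoint and all Day 208 analyses precede Visit 8. AEs reported by subjects are collected in both visit modes. The 135 µg and placebo arms have the same Visit 8 arrangements, so the contrast between them is not touched by this link.

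**The case against.** A reader might infer that AE rates to Day 545 differ between arms by construction, or that they are inflated 1.09-, 1.35- or 1.83-fold in the 180 µg arm at r = 10, 30 or 50%. The protocol does not support either reading. In-person is the preferred mode in every arm, none of the stated reasons for a remote visit depends on arm, and at r = 0 the gap vanishes. The ratios (98.3/90, 94.8/70, 91.3/50) are upper bounds on Visit 8 test coverage, not on AE rates. They assume that all 81 booster subjects attend Visit 8 in person whatever r is. But 81 is a maximum, combining is advisory, and a remote Visit 8 followed by a separate Visit 9 is allowed. That separate Visit 9 includes no chemistry or hematology, so it would not restore those tests.

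Further points on that side stand:
- The examination is done only when a symptom is reported, and symptoms are recorded as AEs in either mode. What is lost is mainly silent laboratory findings.
- Laboratory changes are otherwise analysed descriptively, and only clinically relevant ones become AEs.
- By Day 208, 232 of 246 subjects (94.3%) already had some solicited or unsolicited AE, so the any-AE category can hardly move.
- The dose was chosen on Day 208 results, and the possible bias adds events to that dose; it would not conceal harm there.
- Laboratory denominators and tables of visit mode are ordinary SAP content, so their absence from the protocol is not a fault.

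What remains is that the protocol itself fixes both the schedule that links Visit 8 to an arm-specific visit and the Day 545 comparison that the link can reach.

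**Conclusion.** The point holds as a possibility of unequal ascertainment, not as a demonstrated bias. The protocol allows findings that need a Visit 8 blood or urine sample to be sought more fully in the 180 µg arm, when sites know who belongs to it, and section 9.4 does not separate such findings in the comparison to Day 545.

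The coverage gap is at most 0.83 × r. The excess in subject-level rates of unsolicited AEs is at most about 0.5–2.5 points at r = 30%, and less where subjects already have an AE in the category. Both r and the 2–10% finding rate are assumptions. Frequent false significance is unlikely; the likelier harm is a modest distortion of the Month 18 safety profile of the 180 µg dose against the other two arms.

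**What to change.** In section 9.4, keep the planned comparison up to Day 545 and add one supplementary between-arm comparison of unsolicited AEs. It should exclude, in all arms alike, findings first detected only by in-person Visit 8 laboratory tests (including urinalysis and the Lyme screen) or examination. Section 8.5 already requires laboratory results and their clinical relevance in the eCRF, so laboratory-derived events can be traced.

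Restricting the comparison to subjects with an in-person Visit 8 is not an equivalent. Visit mode arises after randomisation and may depend on arm, so conditioning on it could bring in a new imbalance.

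Support the comparison, in the SAP if preferred, with Visit 8 mode tabulated by arm and with subjects actually tested as the denominator for Visit 8 laboratory and Lyme results. The mode table shows at once whether r was large enough to matter.

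The cost is a few extra tables and no new procedures. The supplementary comparison leaves out some true laboratory events, which is why it should stand beside the planned one and not replace it.

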4.2.4 Number of subjects and study centres

Overall, a total of approximately 250 healthy subjects aged 18 to 65 years^{*} were to be enrolled into the Main Study Phase. Subjects were to be enrolled in two age groups (18-49 years[†] and 50-65 years[‡]) in a ratio of approximately 2:1. In the Booster Phase eligible subjects from the Main Study Phase from the 180 µg treatment group will be continued. No minimal or maximal number of subjects is defined for the Booster Phase. Based on previously observed relevant protocol deviations and dropout rates, the number of participants are estimated to be a maximum of 81 subjects.

Five study centers in Lyme disease endemic areas in the US were selected to participate in this study. The enrollment was stopped as soon as the required number of subjects was reached.

4.2.5 Timely conduct of the study

Study start of the Main Study Phase was July 2019. Study start of the Booster Phase is expected in January 2021.

4.2.6 Study duration

Study duration per subject in the Main Study Phase is approximately 20 months:

- Screening period: max. 21 days
- Treatment period: 6 months (+/- 7 days)
- Follow-up period: 12 months (+/- 28 days) after the third vaccination

Overall study duration of the Main Study Phase is estimated to be 22 months.

Study duration per subject in the Booster Phase is a maximum of approximately 13 months.

Study duration per subject in the Main Study Phase and Booster Phase together is estimated to be a maximum of approximately 33 months.

Overall study duration (i.e., First-Subject-In to Last-Subject Out/ end of Booster Phase) is estimated to be approximately 37 months.

The end of the study is defined as the date of the last visit performed by the last subject.

